6.2.3 End of trial and follow-up period

For all patients who successfully complete the study according to the protocol a follow-up visit (Visit 8) with the patient should be done by the investigator at the end of the follow-up period of 14 days.

Visit 8 (follow-up visit)

- Vital signs
- Body weight measurement
- BP measurement and orthostatic blood pressure test should always be done before taking any blood samples.
- Collection of urine and blood for laboratory testing.
- Home blood glucose monitoring
- Documentation of any adverse events.
- Documentation of concomitant therapies

Patients discontinuing trial medication early from the trial

In general patients should be encouraged to re-start study medication in case of temporary treatment interruptions. If the duration of interruption is more than 7 days, this should be recorded in the "Study Medication Temporary Discontinued/re-started" eCRF.

For the analysis of this trial it is absolutely crucial that all planned assessments are done as planned, even if patients discontinue trial treatment. Patients who discontinue treatment prematurely and who do not withdraw their informed consent must therefore be followed up for the intended regular treatment period. All assessments related to the primary and secondary endpoints must be performed as if the patient would have remained on treatment.

Proprietary confidential information.

© 2016 Boehringer Ingelheim International GmbH or one or more of its affiliated companies. All rights reserved.

This document may not - in full or in part - be passed on, reproduced, published or otherwise used without prior written permission.

For patients who stop study medication permanently prior to completion of 24 weeks of treatment and who are willing to be followed up, the following should be performed whenever possible:

- Premature treatment discontinuation (PTD) visit should be performed within 7 days of last intake of study drug or as soon as possible including all examinations and assessments that are part of the Visit 7.2. If the PTD visit occurs within the time window of a scheduled visit, the PTD visit will replace the scheduled visit.
- Subsequently, a follow-up visit (Visit 8 procedures) should be conducted within 14 days of the PTD visit that replaces the next visit according to the visit schedule.
- Thereafter, patients would be followed up according to the visit schedule.
- Visit 7.2 will be the last visit for these patients. Follow-up Visit 8 does not need to be performed.

The last per study contact should be at Visit 7.2. If determined by investigator as necessary for patient safety, new antidiabetic medication regimen can be started immediately after discontinuation and must be recorded in eCRFs.

If a patient is not able to attend a study visit, the study staff should contact him/her (or someone designated – e.g. family member or personal physician) to inquire about medical information pertaining to adverse events, particularly primary and key secondary outcome events, and/or mortality, until the end of the study. Alternatively, data should be collected from medical records.

For patients who discontinue treatment prematurely but do not wish to follow the visit schedule, the following should be performed whenever possible:

- Visit 7.2 should be performed within 7 days of last intake of study drug.
- Subsequently, a follow-up visit (Visit 8 procedures) should be conducted within 14 days of the premature discontinuation visit.

If this patient withdraws consent, then the last per study contact will be Visit 8.

Patients who withdraw consent

Patients who withdraw consent during the trial should perform Visit 7.2 within 7 days of last intake of study drug. A follow-up visit (Visit 8 procedures) should be conducted within 14 days of the premature discontinuation for their safety.

The following procedures should be performed at Visit 8.

- Vital signs

Proprietary confidential information.

© 2016 Boehringer Ingelheim International GmbH or one or more of its affiliated companies. All rights reserved.

This document may not - in full or in part - be passed on, reproduced, published or otherwise used without prior written permission.

- Body weight measurement
- BP measurement and orthostatic blood pressure test should always be done before taking any blood samples.
- Collection of blood and urine samples for safety laboratory evaluation.
- Documentation of any adverse events.
- Documentation of concomitant therapies

A patient who reverses the decision to withdraw consent should be re-consented with the latest version and will continue the visit schedule according to the date of randomisation.

Proprietary confidential information.

© 2016 Boehringer Ingelheim International GmbH or one or more of its affiliated companies. All rights reserved.

7. STATISTICAL METHODS AND DETERMINATION OF SAMPLE SIZE

7.1 STATISTICAL DESIGN - MODEL

This is a multi-centre, multi-national, randomised, parallel-group, double-blind, placebo-controlled trial to investigate the effect of (10 mg/25 mg) of empagliflozin and placebo after 24 weeks treatment on glucose control, BP and body weight in hypertensive black/African American patients with T2DM. The randomisation will be performed stratified by screening HbA1c values ($<8.5\%$, $\geq 8.5\%$), renal function at screening ($\text{eGFR} \geq 120 \text{ ml/min/1.73m}^2$, $\text{eGFR} 120\text{-}60 \text{ ml/min/1.73m}^2$, $\text{eGFR} \leq 60 \text{ ml/min/1.73m}^2$) and pretreatment with Metformin at screening (yes/no).

Based on experiences with the primary endpoints in other trials and based on literature data, the HbA1c change from baseline, and change from baseline in BP are regarded as normally distributed. Therefore, a restricted maximum likelihood estimation based on mixed-effect model for repeated measures analysis or an analysis of covariance (ANCOVA) approach can be used.

With regard to efficacy and safety endpoints, the term "baseline" refers to the last observed measurement prior to administration of any randomised study medication.

7.2 NULL AND ALTERNATIVE HYPOTHESES

Primary Hypotheses

The confirmatory analyses will compare empagliflozin to placebo. The following hierarchical multiple testing procedure will be used to evaluate superiority for the primary endpoint followed by the evaluation of superiority of the key secondary endpoints, while maintaining the overall probability of a type I error at 0.05. The primary endpoint of change from baseline to 24 weeks in HbA1c along with the key secondary endpoints change from baseline in mean 24-hour ambulatory SBP at 12 weeks of treatment, change from baseline in mean trough ambulatory SBP at 12 weeks of treatment, change from baseline in body weight in kg at week 24 of treatment, and change from baseline in trough seated SBP at 12 weeks of treatment, will be tested in the following pre-specified hierarchical sequence, to address issues of multiplicity. Proceeding onto the next step in the sequence relies upon rejecting H_0 in the previous step, a 'success'. Each step will only be considered confirmatory if all previous steps were 'successful'. If any of the previous steps were not successful, the tests of the subsequent steps have to be interpreted in an exploratory sense. This procedure allows testing each step at the two-sided alpha-level of 5%:

1. change from baseline in HbA1c at 24 weeks of treatment
2. change from baseline in mean 24-hour ambulatory SBP at 12 weeks of treatment
3. change from baseline in mean trough ambulatory SBP at 12 weeks of treatment
4. change from baseline in body weight in kg at week 24 of treatment
5. change from baseline in trough seated SBP at 12 weeks of treatment

Proprietary confidential information.

© 2016 Boehringer Ingelheim International GmbH or one or more of its affiliated companies. All rights reserved.

This document may not - in full or in part - be passed on, reproduced, published or otherwise used without prior written permission.

At each of the 5 stages of the hierarchical sequence the hypotheses will be tested as described below:

$H_{0,1}$: No difference in mean endpoint between empagliflozin and placebo

$H_{1,1}$: A difference in mean endpoint between empagliflozin and placebo

7.3 PLANNED ANALYSES

The statistical analysis will be based on the following populations.

Treated Set

The treated set will consist of all patients who were randomised and treated with at least one dose of trial medication.

Full Analysis Set

The full analysis set (FAS) will consist of all randomised patients who were treated with at least one dose of study drug and had a baseline and at least one on-treatment HbA1c measurement

Per Protocol Set

The per-protocol set (PPS) will consist of all randomised patients who are part of the FAS but who do not have any important protocol violations (IPV) leading to exclusion. Further details on the definition of the PPS and the definition of IPV's will be provided in the TSAP.

7.3.1 Primary analyses

Mean changes from baseline for HbA1c up to 24 weeks of treatment will be analyzed using a restricted maximum likelihood (REML)-based repeated measures approach on the FAS data set. Patients will be analysed according to the treatment group they are randomised to. Analyses will include the fixed, categorical effects of treatment, pre-treatment with Metformin at screening, renal function at baseline, visit, and treatment-by-visit interaction, as well as the continuous, fixed covariates of baseline HbA1c and baseline HbA1c -by-visit interaction. An unstructured (co)variance structure will be used to model the within patient measurements. If the model first fails to converge using an unstructured (co)variance structure, then a hierarchical approach is applied until a (co)variance structure is obtained where the model converges. Therefore the following (co)variance structures are tested according to the pre-specified order: (1) unstructured, (2) Toeplitz, (3) variance components, (4) compound symmetry. As soon as one model converges this will be the final model used, therefore no further testing of subsequent (co)variance structures is required. The Kenward-Roger approximation will be used to estimate denominator degrees of freedom. Significance tests will be based on least-squares means using a two-sided $\alpha = 0.05$ (two-sided 95%

Proprietary confidential information.

© 2016 Boehringer Ingelheim International GmbH or one or more of its affiliated companies. All rights reserved.

This document may not - in full or in part - be passed on, reproduced, published or otherwise used without prior written permission.

confidence intervals). The primary treatment comparisons will be the contrast between treatments at the endpoint visit at 24 weeks of treatment.

For the key secondary endpoint change from baseline in mean 24-hour ambulatory SBP at 12 weeks of treatment an ANCOVA comparing the change from baseline in mean 24-hour ambulatory SBP at 12 weeks of treatment will be used as primary analysis on the FAS using last observation carried forward (LOCF) for missing ABPM assessments.

The statistical model will be the following:

change from baseline in 24-hour ambulatory SBP at 12 weeks =

overall mean + baseline 24-hour ambulatory SBP + treatment + pre-treatment with Metformin + renal function + HbA1c + random error

‘Treatment’, ‘pre-treatment with Metformin’, and ‘renal function’ are fixed classification effects and ‘baseline 24-hour ambulatory SBP’ and ‘HbA1c’ are fixed covariates. The random error is assumed to be normally distributed with mean 0 and unknown variance σ^2 .

A similar ANCOVA models on the FAS using LOCF for missing ABPM assessments will be performed for the change from baseline in mean trough ambulatory SBP at 12 weeks of treatment just replacing the relevant key secondary endpoint’s baseline and 12 week assessments in the model.

For the key secondary endpoints change from baseline in body weight in kg at week 24 of treatment and change from baseline in trough seated SBP at 12 weeks of treatment a restricted maximum likelihood estimation based on mixed-effect model for repeated measures for mean changes from baseline will be used on the FAS observed case analysis set to obtain adjusted means for the treatment effects. These models will include the same discrete fixed effects as the model for the primary endpoint and baseline HbA1c as a continuous fixed effect. Furthermore these models will include the interaction between visit and treatment, and an interaction between visit and baseline measurement of the key secondary endpoint as well as the corresponding baseline measurements of the key secondary endpoint as continuous fixed effect. The covariance approach for this model will be the same as for the primary endpoint. The Kenward-Roger approximation will be used to estimate the denominator degrees of freedom. The primary treatment comparisons will be the contrast between treatments at the 12 week visit for trough seated SBP and 24 week visit for the body weight and significance tests will be based on least-squares means using a two-sided $\alpha = 0.05$ (two-sided 95% confidence intervals).

All analyses will be implemented using SAS®.

Proprietary confidential information.

© 2016 Boehringer Ingelheim International GmbH or one or more of its affiliated companies. All rights reserved.

This document may not - in full or in part - be passed on, reproduced, published or otherwise used without prior written permission.

7.3.2 Secondary analyses

The primary endpoint analysis method as detailed in [Section 7.3.1](#) will be repeated for the PPS.

The primary endpoint will as well be analysed using an ANCOVA model in the FAS. The model will include randomised treatment, pre-treatment with Metformin, and renal function at baseline as categorical fixed effects, and baseline HbA1c as continuous covariate. Missing HbA1c data will be imputed using the LOCF approach.

The term "baseline HbA1c" refers to the last assessment prior to the administration of any randomised study medication.

The model for the primary endpoint is as follows:

$$\begin{aligned} \text{HbA1c change from baseline at week 24} = & \text{overall mean} \\ & + \text{HbA1c at baseline} \\ & + \text{treatment} \\ & + \text{renal function} \\ & + \text{pretreatment with Metformin} \\ & + \text{random error} \end{aligned}$$

This model includes effects accounting for the following sources of variation: 'HbA1c at baseline', 'renal function' at baseline, 'pretreatment with Metformin' at screening, and 'treatment'. 'Treatment', 'renal function', and 'pretreatment with Metformin' are fixed classification effects and 'HbA1c baseline' is a linear covariate. The random error is assumed to be normally distributed with mean 0 and variance σ^2 . This secondary analysis will be performed on the FAS with treatment assignment as randomised. Missing data will be imputed using the LOCF approach.

For the key secondary endpoints change from baseline in body weight in kg at week 24 of treatment and change from baseline in trough seated SBP at 12 weeks as well an ANCOVA model will be calculated on the FAS. The model for the change from baseline includes 'treatment', 'renal function' at baseline, 'pretreatment with Metformin' at screening as fixed categorical effects, and HbA1c at baseline, and baseline trough seated SBP or baseline body weight in kg respectively, as linear covariate. Missing data will be imputed using the LOCF approach.

The other continuous secondary endpoints as listed in [Section 5.1.1](#) will be analysed on the FAS as follows:

Proprietary confidential information.

© 2016 Boehringer Ingelheim International GmbH or one or more of its affiliated companies. All rights reserved.

This document may not - in full or in part - be passed on, reproduced, published or otherwise used without prior written permission.

The continuous secondary endpoints will be analysed using similar models as used for the primary analyses for the key secondary endpoints. [REDACTED]

7.3.3 Safety analyses

Adverse events will be coded using the Medical Dictionary for Regulatory Activities (MedDRA) coding dictionary. Standard BI summary tables and listings will be produced. All adverse events with an onset between start of treatment and end of the residual effect period (REP), a period of ≤ 7 days after the last dose of trial medication, will be assigned to the treatment period for evaluation.

All treated patients will be included in the safety analysis. In general, safety analyses will be descriptive in nature and will be based on BI standards. No hypothesis testing is planned. Statistical analysis and reporting of adverse events will concentrate on treatment-emergent adverse events. To this end, all adverse events occurring between start of treatment and end of the REP will be considered 'treatment-emergent'. The REP is defined as ≤ 7 days following last intake of trial medication. Adverse events that start before first drug intake and deteriorate under treatment will also be considered as 'treatment-emergent'. Frequency, severity, and causal relationship of adverse events will be tabulated by system organ class and preferred term after coding according to the current version of the MedDRA.

Laboratory data will be analysed both quantitatively as well as qualitatively. The latter will be done via comparison of laboratory data to their reference ranges. Values outside the reference range as well as values defined as clinically relevant will be highlighted in the listings. Treatment groups will be compared descriptively with regard to distribution parameters as well as with regard to frequency and percentage of patients with abnormal values or clinically relevant abnormal values. Vital signs, physical examinations, or other safety-relevant data observed at screening, baseline, during the course of the trial and at the end-of-trial evaluation will be assessed with regard to possible changes compared to findings before start of treatment.

7.3.4 Interim analyses

No interim analyses are planned.

7.3.6 Pharmacodynamic analyses

Not applicable.

Proprietary confidential information.

© 2016 Boehringer Ingelheim International GmbH or one or more of its affiliated companies. All rights reserved.

This document may not - in full or in part - be passed on, reproduced, published or otherwise used without prior written permission.

7.3.7 Pharmacogenomic analyses

Not applicable.

7.4 HANDLING OF MISSING DATA

Mixed Model Repeated Measures (MMRM) models and ANCOVA models including a LOCF imputation of missing data are used like discussed above in [Section 7.3.1](#) and [Section 7.3.2](#). The mixed effect model will handle missing data based on a likelihood method under the "missing at random assumption". Efficacy data will be censored at the date of first intake of antidiabetic rescue medication for all analyses, i.e., will be set to missing, if not explicitly stated otherwise.

Blood pressure data will additionally be censored from the day of change in antihypertensive therapy.

With respect to safety evaluations, it is not planned to impute missing values.

Further details will be provided in the TSAP.

7.5 RANDOMISATION

The trial will be performed as a double-blind design with respect to study medication. Patients will be randomised to the two study treatments in a 1:1 ratio. The randomisation will be performed in blocks. The block size will be reported in the Clinical Trial Report (CTR). The randomisation will be stratified by the following factors:

- screening HbA1c value ($<8.5\%$, $\geq 8.5\%$)
- renal function at screening ($eGFR \geq 120$ ml/min/1.73m², $eGFR$ 120-60ml/min/1.73m², $eGFR \leq 60$ ml/min/1.73m²)
- pretreatment with Metformin at screening (yes/no)

The randomisation of patients to the treatment groups will be performed via an IRT system. BI will arrange for the randomisation as well as packaging and labelling of study medication. The randomisation list will be generated using a validated system, which involves a pseudorandom number generator and a supplied seed number so that the resulting allocation of medication numbers to treatment is both reproducible and non-predictable.

7.6 DETERMINATION OF SAMPLE SIZE

In order to ensure that each comparisons of empagliflozin and placebo with respect to HbA1c, mean systolic ABPM blood pressure and body weight have a power of at least 80%, 64 patients plus an additional 20% drop-out rate, resulting in 77 patients per arm are required per treatment group. This is derived from the assumption that the difference in change from baseline compared to placebo in 24-hour SBP is 5 mmHg with a standard deviation of 10

Proprietary confidential information.

© 2016 Boehringer Ingelheim International GmbH or one or more of its affiliated companies. All rights reserved.

This document may not - in full or in part - be passed on, reproduced, published or otherwise used without prior written permission.

mmHg (resulting in a power of 80%), and the difference in body weight is 2 kg with a standard deviation of 2.3kg (resulting in a power of 99%). With this sample size the power to detect a 0.6% difference in HbA1c with a standard deviation of 1.1% will be >85%.

The planned treatment group sizes are considered as sufficient for the confirmatory evaluation of efficacy and the descriptive assessment for safety, tolerability and PK.

Proprietary confidential information.

© 2016 Boehringer Ingelheim International GmbH or one or more of its affiliated companies. All rights reserved.

This document may not - in full or in part - be passed on, reproduced, published or otherwise used without prior written permission.

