
Statistical methods:
 
For change from baseline in HbA1c up to 24 weeks of treatment a restricted maximum likelihood estimation based on a mixed-effect model for repeated measures analysis will be used to obtain adjusted means for the treatment effects on the full analysis set (FAS). This model will include treatment, visit, and the stratification factors renal function at baseline, and pretreatment with Metformin at screening as discrete fixed effects, baseline HbA1c as a continuous fixed effect, and interaction between visit and treatment, and an interaction between visit and baseline HbA1c. The primary treatment comparisons will be the contrast between treatments at the endpoint visit at 24 weeks of treatment.
 
For the change from baseline in trough seated SBP up to 12 weeks of treatment and the change from baseline in body weight in kg at 24 weeks as well a restricted maximum likelihood estimation based on mixed-effect models for repeated measures analysis will be used to obtain adjusted means for the treatment effects on the FAS. These models will include the same discrete fixed effects as the model for the primary endpoint and baseline HbA1c as continuous fixed effect, as well as interaction between visit and treatment, and interaction between visit and baseline measurement of the key secondary endpoint, as well as the corresponding baseline measurements of the key secondary endpoint as continuous effect. The primary treatment comparisons will be the contrast between treatments at the 12 week visit for seated SBP and 24 week visit for body weight.
 
The key secondary endpoint change from baseline in 24-hour ambulatory SBP and change from mean trough ambulatory SBP at 12 weeks will be analyzed by using an analysis of covariance (ANCOVA) approach in the FAS with last observation carried forward (LOCF) for missing data. The model will include randomised treatment, renal function at baseline, pretreatment with Metformin at screening as discrete fixed effects and the baseline of the key secondary endpoint and HbA1c at baseline as continuous fixed effects.
 
The overall type I error across the hypotheses tests in the confirmatory analysis will be maintained at a level of $\alpha \leq 0.05$ using a hierarchical testing sequence. The sample size of 154 patients per group was derived (assuming n=64 per groups plus a 20% drop-out rate) based on the requirement that the comparisons of empagliflozin versus placebo with respect to the HbA1c, BP and body weight should have a power of at least 80% at the two-sided α level of 5%.
 
Explorative statistical models and descriptive statistics will be used for the other secondary endpoints and safety parameters.
			

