3.3 SELECTION OF TRIAL POPULATION

Approximately 700 patients will be screened for the trial in US. About 85 trial centres will be participating to ensure that approximately 154 patients are randomised to trial treatment (77 to each treatment group). The intention is that at least 2 patients should be randomised at each trial centre. Investigators who fail to screen at least one patient in the first 6 weeks of the trial may be re-evaluated for further participation. If enrolment is delayed, additional centres may be recruited.

Permission to randomise more than 8 patients per site must be obtained from the TCM at Boehringer Ingelheim. This will only be allowed after a careful review of the enrolment status.

Screening of patients for this trial is competitive, i.e. screening for the trial will stop at all centres when such a number of patients has been screened and it is anticipated that a

Proprietary confidential information.

© 2016 Boehringer Ingelheim International GmbH or one or more of its affiliated companies. All rights reserved.

This document may not - in full or in part - be passed on, reproduced, published or otherwise used without prior written permission.

sufficient number of patients will be randomised to trial treatment. Investigators will be notified when the appropriate number of patients has been screened and screening is complete, and will not be allowed to recruit additional patients for this study. Patients who have completed Visit 1 procedures prior to notification of the termination of recruitment will be allowed to continue in the study, if they meet all entry criteria and they are able to follow the visit schedule specified in this protocol.

The check for patient eligibility will be based upon a complete medical history including a physical examination and clinical laboratory tests. Judgement of the clinical relevance of a concomitant disease is at the discretion of the investigator. Conditions under therapy are always clinically relevant.

A log of all patients included into the study (i.e. having given informed consent) will be maintained in the ISF at the investigational site irrespective of whether they have been treated with investigational drug or not.

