- The next day when the patient returns to the clinic (within 23:30-24 hours of the beginning of the test), prompt the monitor to take a Conclusion of Test reading. If an invalid reading occurs for the Conclusion of Test reading, continue to trigger a manual reading until a valid reading is registered. The monitor will then be removed and the time of the Conclusion of Test will be recorded.
- If ABPM was successful, procedures for Visit 5.2 can be conducted on the same day after the ABPM device is removed and trough seated blood pressure measurement is taken. If conducted on the same day, procedures for Visit 5.2 should be done prior to administering study medication.
- If the first ABPM attempt was unsuccessful (failed QC), a repeat reading should be taken within 2 days. Patient having two technically unsuccessful ABPM sessions may continue with Visit 5.2. Procedures for Visit 5.2 can be conducted on the same day after the ABPM device is removed and trough seated blood pressure measurement is taken.
- Allow the patient to rest for at least 15 minutes after the monitor is removed. Then take a seated blood pressure measurement. Record the time of this measurement. This should be done prior to administering study medication.
- Administer dose of study medication.
- For further instructions for ABPM measurements, please see [Section 5.1.2](#).
- Instruct patients NOT to take study medication on the morning of the next trial visit.

Visit 5.2

- BP and orthostatic blood pressure test should always be done before taking any blood samples.
- Collection of urine and blood for laboratory testing must be performed prior to administration of study medication at each visit.
- PK trough sample should be collected within 30 minutes prior to intake of study medication.
- Collect returned medication.
- New medication kit must be dispensed according to the [Flow Chart](#), and the IRT system must be contacted to obtain medication kit numbers to be dispensed.
- Patients should be reminded about the importance of following the agreed diet and exercise plan. Patients should be given a food log to be completed for three consecutive days prior to Visit 7.2 as indicated in the Flow Chart.
- Provide HBGM equipment/supplies and instruct patient on the correct use of HBGM.

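### Protocol 7.6 reaches 77 per arm as 64 × 1.2; a 20% drop-out then leaves about 62 per arm, with unadjusted power of about 79% for 24-hour SBP, just under the promised 80%

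*Protocol*

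**What the plan says.** Protocol Section 7.6 asks for at least 80% power, at the two-sided 5% level, for HbA1c, mean 24-hour ambulatory SBP and body weight. It derives the number as "64 patients plus an additional 20% drop-out rate, resulting in 77 patients per arm are required per treatment group". The assumptions are:

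- 24-hour SBP: difference 5 mmHg, SD 10 mmHg, stated power 80%.
- Body weight: difference 2 kg, SD 2.3 kg, stated power 99%.
- HbA1c: "With this sample size the power to detect a 0.6% difference in HbA1c with a standard deviation of 1.1% will be >85" (per cent).

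Section 3.3 agrees on the total and the split: "approximately 154 patients are randomised to trial treatment (77 to each treatment group". The table at the start of the synopsis also has 154 in total and 77 per treatment. The statistical methods part of the synopsis differs: "The sample size of 154 patients per group was derived (assuming n=64 per groups plus a 20% drop-out rate".

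The endpoint that sets the size is "change from baseline in mean 24-hour ambulatory SBP at 12 weeks of treatment", second in the testing sequence of Section 7.2. Section 7.6 gives no time point for the 20% drop-out.

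**The concern.** A drop-out rate is a fraction of the patients randomised. To keep n evaluable patients after losing a fraction p, one randomises n / (1 − p). Multiplying by (1 + p) gives too few, and here the stated number matches the multiplication.

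A reader of Section 7.6 will take it that 77 per arm can lose 20% and still give 80% power for 24-hour SBP. That endpoint has no margin, because 64 is the smallest number per arm that reaches 80% by t-test. It is also the first key secondary test: if it fails, the tests of trough ambulatory SBP, body weight and trough seated SBP become exploratory. The synopsis wording is a separate slip that, read literally, doubles the trial to 308 patients.

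**Working it through.** **Inputs.** All are from Protocol 7.6 except the allocation ratio of 1:1 (Section 7.5) and the two-sided 5% level (Section 7.2). Differences and SDs are as listed above; 64 per arm, 20% drop-out, 77 per arm.

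**Method.** Two-sample t-test with n per arm, 2n − 2 degrees of freedom and noncentrality δ / (σ√(2/n)). The normal approximation is shown where it matters.

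**Step 1: reproduce the plan's 64.** For SBP at n = 64 the noncentrality is 5 / (10 × √(2/64)) = 2.83, and power is 80.1%. At n = 63 it is 79.5%, so 64 is the smallest n that reaches 80%. The normal approximation gives 63 (80.1%).

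**Step 2: which n do the stated powers belong to?**

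| Endpoint | Stated | n = 64 | n = 77 |
|---|---|---|---|
| 24-hour SBP | 80% | 80.1% | 86.9% |
| HbA1c | >85% | 86.5% | 92.0% |
| Body weight | 99% | 99.8% | >99.9% |

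The SBP figure fits 64 and not 77. So 64 is the evaluable number.

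**Step 3: the inflation.**

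- 64 × 1.2 = 76.8, rounded up to 77: matches the protocol.
- 64 / (1 − 0.20) = 80: does not match.
- 77 × 0.8 = 61.6 evaluable, against 64 needed.
- Loss that still leaves 64: 13 of 77 = 16.9%. For the normal approximation, which needs 63: 14 of 77 = 18.2%.

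**Step 4: power after a 20% loss.**

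| Evaluable per arm | SBP, t-test | SBP, normal | HbA1c, t-test | Body weight, t-test |
|---|---|---|---|---|
| 62 | 78.9% | 79.5% | 85.4% | 99.8% |
| 61.6 | 78.6% | 79.2% | 85.2% | 99.8% |
| 61 | 78.2% | 78.9% | 84.8% | 99.7% |

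**Step 5: what would restore 80% for SBP.** The documents give neither the loss at week 12 nor the correlation of the covariates with the change, so both are varied as assumptions.

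- *Smaller loss.* At an assumed 10% (77 × 0.9 = 69.3 per arm), t-test power is 83.2%.
- *Smaller SD.* At 61.6 per arm, 80% needs an SD of about 9.83. If 10 is the unadjusted SD, the covariate correlation needed is √(1 − 0.983²), about 0.19. At 61 per arm the figures are 9.78 and 0.21; at 62 they are 9.86 and 0.17.

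**The case against.** The arithmetic is not in dispute. The case against is about how much it shows.

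- **Adding 20% to 64 is what the sentence says.** This explains how 77 arose. But the 20% is called a drop-out rate, and on that reading 77 absorbs only 16.9%, which the protocol does not say.
- **The planned test is an ANCOVA.** Protocol 7.3.1 models the change as "overall mean + baseline 24-hour ambulatory SBP + treatment + pre-treatment with Metformin" plus renal function and HbA1c. A modest correlation would remove the shortfall. This stands, but only if SD 10 is not already a residual SD, and Section 7.6 does not say.
- **SBP is read at week 12 of 24.** Loss by then may be below 20%. This also stands as a possibility. Other losses work the other way. A repeat session is allowed, but after that "Patient having two technically unsuccessful ABPM sessions may continue with Visit 5.2". Section 7.4 adds "Blood pressure data will additionally be censored from the day of change in antihypertensive therapy", on top of censoring at antidiabetic rescue.
- **LOCF may fill gaps.** SAP 6.6.2.4 carries forward on-treatment values, and SAP 7.5.1 notes a single post-baseline ambulatory assessment up to week 12, so nothing earlier on treatment exists to carry. Interpolation using the later ABPM could recover some patients, but the SAP does not make clear whether baseline may serve as the earlier value.
- **HbA1c and body weight use MMRM**, which keeps the on-treatment data of patients who drop out later. The figures of 85.2% and 99.8% count those patients as contributing nothing. They should be labelled as unadjusted t-test figures.
- **The gap is small.** It is, and recruitment is planned as approximately 154. That limits the importance of the point but does not make the stated figures right.
- **The synopsis slip is visible from its own sentence**, which also gives 64 per group. True, but it is current text and should be corrected.

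**Conclusion.** The point holds and is minor. Under the calculation that reproduces the protocol's 64, 77 per arm does not preserve 80% power for 24-hour SBP after the protocol's own 20% drop-out. Power is about 79%: 78.6% by t-test, or 78.2% to 78.9% for 61 to 62 per arm, and 79.2% by normal approximation at 61.6. The deficit against 64 / 0.8 is 3 patients per arm.

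This rests on an unadjusted two-sample comparison, SD 10 mmHg, and a full 20% of patients without a usable week-12 value. It does not show that the planned ANCOVA is underpowered; a smaller week-12 loss or a modest gain from the covariates would close the gap. HbA1c and body weight stay well above 80%. The figure of 154 per group in the synopsis is an error on any reading.

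**What to change.** Restate the figures in Section 7.6 and the synopsis; enrol no more patients.

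1. Replace the unconditional claim of at least 80% power, so that it does not stand beside a figure of about 79%. Suggested text: *77 patients per arm (154 in total) is 64 × 1.2. Under an unadjusted two-sample t-test, 64 per arm remain evaluable with up to about 17% loss, giving 80% power for 24-hour SBP. At 20% loss about 62 per arm remain, with power of about 79% for 24-hour SBP, about 85% for HbA1c and over 99% for body weight.*
2. State the time point to which the 20% refers, and whether SD 10 mmHg is a residual SD after adjustment for the ANCOVA covariates.
3. In the statistical methods part of the synopsis, give 77 per group (154 in total) in place of 154 per group.

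The cost is two or three sentences in Section 7.6 and the matching synopsis text. Analysis and conduct are unchanged.
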